- **Study Design:** A randomized, double-blind, placebo-controlled, parallel-group study of flexible dose mixed salts amphetamine (5-60 mg) adjunctive to antidepressant therapy among adult outpatients with major depressive disorder responding inadequately to current antidepressant therapy.

Fig. 1: Treatment Groups

Visit	Phase	Weeks	Group	Group	Procedures
		on med	1	2	
V1		Scr			Inclusion/Exclusion
V2		0			Baseline measurement + disp.
V3	Ι	1	MSA	PBO	Measure effect of 1 week on study med + disp.
V4	Ι	2	MSA	PBO	Measure effect of 2 weeks on study med + disp.
V5	Ι	3	MSA	PBO	Measure effect of 3 weeks on study med + disp.
V6	II	4	MSA	MSA	Measure effect of 3 weeks on study med + disp.
V7	II	5	MSA	MSA	Measure effect of 3 weeks on study med + disp.
V8	II	6	MSA	MSA	Measure effect of 3 weeks on study med
V9		(8)			Safety follow-up

Fig. 2: Study Design Overview

The treatment phase of the study consists of 2 phases (21 treatment days per phase). Study Phase 1 will consist of visits 2 (baseline) through 5. Study Phase 2 will consist of visits 6 through 8. There will be a follow-up visit 2 weeks following visit 8. There is a one-week interval between study visits, with a scheduling window of \pm 3 days allowed.

Mixed salts amphetamine is FDA-approved for Attention Deficit-Hyperactivity Disorder (ADHD) and superior in efficacy to placebo; therefore, comorbid ADHD will be statistically controlled as a continuously-variable covariate, but will not be considered an exclusionary condition.

The primary analysis will be a repeated measures analysis of variance using a mixed-effects model (PROC MIXED-MMRM). The primary outcome measure will be the MGH-CPFQ total score at baseline and the MGH-CPFQ total score at the end of the trial. The independent variables will be the study visit, the treatment in the previous phase, and treatment assignment. The variance covariance matrix for the repeated measures will be unspecified.

Enrollment Period: The enrollment period is estimated to be 6 months. The last patient is expected to complete the study by March 31, 2010.

Number of Subjects: 40 subjects will be randomized (20 to each treatment arm). Additional subjects may be consented to allow for screen failures. Subjects who terminate early post-randomization will be replaced only sufficiently to ensure a total number of 24 (12 to each treatment arm) evaluable subjects.

Duration of Subjects' Study Participation: There will be a total of 9 study visits over a period of 9 weeks.

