- 11) Pregnant or breastfeeding women.

Study Procedures: Figure 3 shows study procedures to be performed at each visit. No study procedures will be performed until a subject signs the informed consent document.

Screen visit (Visit 1): Medical and psychiatric history will be taken, a physical examination and vital signs will be performed and lab tests done. Lab tests include CBC, CMP, urine drug screen and urine pregnancy test for females of childbearing potential. If a subject has had the required lab tests performed within the past 3 months and can produce the results, lab procedures may be waived at the screening visit for that patient (except urine pregnancy test). The HDRS-17 score upon screening will be used to determine entry eligibility (see inclusion criteria). Beyond the patient's verbal report, we will attempt to obtain medical records (e.g., previous clinician or pharmacy records) to document adequate dose and duration of previous/current ADT.

Study Phase 1

Baseline visit (Visit 2): Screened and eligible subjects will return one week after the screening visit. At this visit (provided entry criteria continue to be met) subjects will be randomized in double-blind fashion to one of two treatment groups:

- Group 1: MSA during both phases; or
- Group 2: PBO during Phase 1 followed by MSA during phase 2

Study drug will be dispensed to the subject in sufficient quantity to last until the next study visit (7 days +/-3).

Study visits 3-5: Following the baseline visit, subjects will return at one-week intervals for study visits 3-5. Study procedures to be performed are reflected in Figure 3. Phase 2 study drug is dispensed at study visit 5.

Study visits 6-8: Subjects will return at one-week intervals for study visits 6-8. Study procedures to be performed are reflected in Figure 3. At visit 8, all subjects will receive instructions for tapering the dose of the MSA to avoid potential difficulties from abrupt discontinuation of the study drug.

Study visit 9: Subjects will return two weeks following visit 8 for a safety follow-up check. Procedures to be performed are reflected in Figure 3.

If a subject withdraws or is terminated early from the study, visit 9 procedures will be performed at the final study visit.

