Study Assessments and Primary Endpoints: The difference in absolute change in score from baseline to endpoint in the MGH-CPFQ between the MSA and the PBO groups is the primary endpoint. Key secondary endpoints will be difference in absolute change from baseline in MADRS score between MSA and PBO, difference in remission rates (MADRS < 11) between MSA and PBO, the change from baseline in total score at endpoint of MGH-CPFQ item analysis, difference in change scores on the CGI-S, CGI-I and QIDS. Safety outcome measures: adverse events, physical examinations, vital signs; blood pressure, orthostatic; EKG; Rush Sexual Inventory (RSI).

Statistical Methods: The randomized sample includes all patients who are randomized. The Safety sample will include those randomized patients who received at least one dose of doubleblind study medication as indicated on the dosing record. The efficacy sample will include those patients in the safety sample who have at least one efficacy evaluation post-randomization. The last observation carried forward (LOCF) data set includes data recorded at a given visit after randomization, or, if no observation is recorded at that visit, data carried forward from the previous postrandomization visit. The LOCF data set is primary, and analysis of the observed case data set also will be conducted.

The primary analysis will compare pooled MGH-CPFQ response rates between PBO and MSA and PBO non-responders. Differences in response rates will be compared using the CMH General Association Test. Descriptive statistics on non-primary groups will be conducted.

This study seeks to estimate the strength of any statistically significant relationship, or effect size, in addition to statistical significance of found treatment effects.

Secondary Endpoints Analysis: Differences in remission (defined as an endpoint MADRS score <11) rates will be compared using the CMH General Association Test. Logistic regression analysis will be performed to explore the relationship between response and patients' demographics and prognostic variables including baseline QIDS score, gender, site, and age, etc. Similar analyses will be performed for remission.

Fig. 3	: Stud	y Proce	dures	Table
--------	--------	---------	-------	-------

			Treatment period 1			Treatment period 2			
Study Visit	V1 Screen	V2 Baseline	V3	V4	V5	V6	V7	V8	V9 F/UP
End of Week	-1	0	1	2	3	4	5	6	8
Day	-7	0	7	14	21	28	35	42	56
Informed consent	Х								
Demographic data	Х								

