Medical and psychiatric history	Х	Х							
SCID	х								
Physical exam	Х								
Vital signs and weight	Х	Х	Х	Х	Х	Х	Х	Х	Х
EKG	Х								Х
Lab tests*, urine pregnancy test** and urine drug screen	х								х
MGH-ATRQ	Х								
Inclusion/exclusion criteria	Х	Х							
Randomization		Х							
Expectation ratings		Х							
Clinician-completed surveys:									
HDRS (17- and 28-item)	Х	Х						Х	
MADRS		Х	Х	Х	Х	Х	Х	Х	
CGI-S	х	Х							
CGI-I			Х	Х	Х	Х	Х	Х	
C-SSRS	х	Х	Х	Х	Х	х	Х	Х	х
Patient-completed surveys:									
MGH-CPFQ	Х	Х	Х	Х	Х	Х	Х	Х	
EWPS	х	Х	Х	Х	Х	х	Х	Х	
Fawcett EPI	Х	Х	Х	Х	Х	Х	Х	Х	
FASD	Х	Х	Х	Х	Х	Х	Х	Х	
HSQ 2.0	Х	Х	Х	Х	Х	Х	Х	Х	
PGI-S	х	Х							
PGI-I			Х	Х	Х	Х	Х	Х	
RSI	Х	Х	Х	Х	Х	Х	Х	Х	
QIDS-16	Х	Х	Х	Х	Х	Х	Х	Х	
SANS	Х	Х	Х	Х	Х	Х	Х	Х	
SDS	Х	Х	Х	Х	Х	Х	Х	Х	
SF-36	Х	Х	Х	Х	Х	Х	Х	Х	
Study drug dispensed		Х	Х	Х	Х	Х	Х	Х	
Study drug accountability			Х	Х	Х	Х	Х	Х	Х
Concomitant therapy	Х	Х	Х	Х	Х	Х	Х	Х	Х
Adverse events	Х	Х	Х	Х	Х	Х	Х	Х	Х

*Including CBC and CMP. If patient can produce lab results for CBC and CMP performed within the past 3 months, screening procedures may be waived. **For females of childbearing potential

- Angst J. (1992). How recurrent and predictable is depressive disorder? In: Montgomery S, Rouillon F, eds. *Long-term treatment of depression perspectives in psychiatry*. Chichester, UK: John Wiley & Sons Ltd., Vol. 3, p.13.
- Carvalho AF, Machado JR & Cavalcante JL (2008). Augmentation strategies for treatmentresistant depression. *Current Opinion in Psychiatry*, 22 : 7–12.
- Chiarello RJ & Cole JO (1987). The use of psychostimulants in general psychiatry. *Archives of General Psychiatry*, 44, 286-295.

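### The MGH-CPFQ is scored twice before study drug, but the stated primary endpoint subtracts one baseline, no pre-drug score is a covariate, and the screening score is unused: precision is lost, without bias

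*Combined protocol and SAP*

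**What the plan says.** - **Endpoint.** Under Statistical Analysis (Study Assessments and Primary Endpoints), the primary endpoint is the MSA-placebo "difference in absolute change in score from baseline to endpoint in the MGH-CPFQ".
- **Model.** The primary-analysis paragraph under Study Design describes a mixed-effects repeated measures model: "The primary outcome measure will be the MGH-CPFQ total score at baseline and the MGH-CPFQ total score at the end of the trial". Its terms are given as follows: "The independent variables will be the study visit, the treatment in the previous phase, and treatment assignment". The only other adjustment named is that "comorbid ADHD will be statistically controlled as a continuously-variable covariate".
- **Schedule.** The row in Fig. 3 reads "MGH-CPFQ Х Х Х Х Х Х Х Х", which covers V1 to V8 and so includes screening and baseline. Study Procedures states: "Screened and eligible subjects will return one week after the screening visit".
- **Baseline.** Fig. 1 gives V2 as "Baseline measurement + disp", and the text below Fig. 2 states: "Study Phase 1 will consist of visits 2 (baseline) through 5". Study drug is first dispensed at V2.
- **Entry.** Inclusion criterion 4 uses the HDRS-17 at screen and baseline. The MGH-CPFQ plays no part in eligibility.
- **A second primary analysis.** Statistical Methods also calls a CMH comparison of MGH-CPFQ response rates primary.

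**The concern.** A single self-rated score contains measurement error and week-to-week fluctuation. Subtracting it carries all of that noise into each subject's change score. Using it as a covariate lets the data choose its weight, so the residual variance is never larger in expectation, apart from a small cost for estimating the coefficient. A second pre-drug score a week earlier may add information on the subject's usual level.

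Both scores precede randomised treatment, and subjects are not selected on this scale, so using them cannot bias the comparison of arms. With 40 randomised and possibly only 24 evaluable, residual variance largely determines the width of the interval. Interval width also matters directly because the plan says it wants to estimate effect size.

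**Working it through.** **The plan's own figure.** There is no power calculation to reproduce. Number of Subjects gives 40 randomised (20 per arm) and at least 24 evaluable (12 per arm). For an unadjusted comparison at two-sided 5% and 80% power, the t-based detectable difference is 0.91 SD of the analysed variable with 20 per arm and 1.20 SD with 12 per arm.

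**Assumed inputs (none is in the plan).** Two-sided 5%; effect 0.7 SD of the endpoint score; an MSA-placebo contrast at one visit; equal variances. Let r12 be the correlation of V1 with V2, r1 that of V1 with the endpoint, and r2 that of V2 with the endpoint. The ADHD covariate is left out of every method alike.

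**Residual variance v, in units of the score variance.**
- Change from V2: 2(1 - r2)
- V2 as covariate: 1 - r2²
- V1 and V2 as separate covariates: 1 - (r1² + r2² - 2·r1·r2·r12)/(1 - r12²)
- V1-V2 mean as covariate: 1 - ((r1 + r2)/2)² / ((1 + r12)/2)

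With all correlations 0.5, these give:
- change from V2: 2 × 0.5 = 1.00
- V2 covariate: 1 - 0.25 = 0.75
- separate V1 and V2: 1 - (0.25 + 0.25 - 0.25)/0.75 = 0.667
- mean: also 0.667

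**Power.** Noncentral t with noncentrality 0.7/√(2v/n) and 2n - 2 - k degrees of freedom, where k is the number of covariates. Each cell reads change score / V2 covariate / V1 and V2 separately.

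| r12, r1, r2 | v | Power %, 20 per arm | Power %, 12 per arm |
|---|---|---|---|
| 0.4, 0.4, 0.4 | 1.20 / 0.84 / 0.771 | 50.4 / 65.3 / 68.9 | 32.2 / 43.1 / 46.0 |
| 0.5, 0.5, 0.5 | 1.00 / 0.75 / 0.667 | 57.8 / 70.2 / 75.1 | 37.5 / 47.2 / 51.6 |
| 0.6, 0.6, 0.6 | 0.80 / 0.64 / 0.550 | 67.4 / 76.9 / 82.8 | 45.0 / 53.4 / 59.5 |
| 0.7, 0.7, 0.7 | 0.60 / 0.51 / 0.424 | 79.5 / 85.5 / 91.1 | 56.2 / 62.9 / 70.8 |
| 0.7, 0.5, 0.5 | 1.00 / 0.75 / 0.706 | 57.8 / 70.2 / 72.7 | 37.5 / 47.2 / 49.3 |
| 0.9, 0.5, 0.5 | 1.00 / 0.75 / 0.737 | 57.8 / 70.2 / 70.9 | 37.5 / 47.2 / 47.7 |
| 0.8, 0.4, 0.5 | 1.00 / 0.75 / 0.750 | 57.8 / 70.2 / 70.1 | 37.5 / 47.2 / 47.0 |

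**Splitting the gain.** At correlation 0.5 and 20 per arm, adjusting for V2 gives 70.2 - 57.8 = 12.4 points and V1 gives 75.1 - 70.2 = 4.9. Over the table at 20 per arm, V1's share runs from 70.1 - 70.2 = -0.1 to 82.8 - 76.9 = 5.9.

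**Mean or separate terms.** In the last row V1 predicts the endpoint only through V2. The mean then gives v = 1 - 0.45²/0.9 = 0.775, against 0.75 for V2 alone. Power at 20 per arm is 68.8% for the mean, 70.2% for V2 alone and 70.1% for separate terms.

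**Cost of estimating the coefficients.** The table charges covariates only for degrees of freedom. Chance imbalance inflates v further, by (N - 3)/(N - 4) for one covariate and (N - 3)/(N - 5) for two. At N = 40 these are 37/36 = 1.028 and 37/35 = 1.057; at N = 24 they are 21/20 = 1.05 and 21/19 = 1.105. Including this at 20 per arm:
- Correlation 0.5 throughout: 57.8 / 69.0 / 72.8%.
- Last row: 57.8 / 69.0 / 67.7%, with the mean at 67.6%.

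On this stricter count V1's share is about -1 to +5 points at 20 per arm and about -2 to +6 at 12 per arm. V2 adjustment still beats the change score in every case computed.

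**Validity.** Simulated type I error, run for the change score, V2 adjustment and V1-V2 mean adjustment, was 4.3% to 5.5%.

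**The case against.** **V2 as baseline is conventional and valid.** Taking the last pre-dose value is standard practice. This stands: a reader might infer that ignoring V1 biases the result, but randomisation protects the change-score comparison and any regression to the mean affects both arms alike.

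**The large figure is not V1's.** A reader might credit the whole 17 points to the unused screening score. About 12 of them come from adjusting for V2 at all. Equal correlation also favours V1, because it makes a score taken a week earlier predict the endpoint as well as V2 does. If correlation decays with time, V1 may add nothing, so a claim that using V1 always narrows the interval is unsupported. This stands and limits the point.

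**The change score may not be the planned analysis.** The mixed model names the baseline total as part of the outcome. If baseline is a repeated response with arm means constrained equal, precision is already like that of V2 adjustment. If the means are unconstrained and data are complete, the contrast equals the change score. The text does not say which applies, and V1 is absent either way. The CMH response-rate test has no direct place for a continuous covariate, so the conflict over the primary analysis has to be settled first. This stands as a condition on the fix.

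**Conclusion.** The point holds as one of efficiency. Two pre-drug MGH-CPFQ scores are scheduled, the stated endpoint subtracts one of them, the listed model terms include neither as a covariate, and V1 enters no analysis.

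Under equal correlations of 0.4 to 0.7, a 0.7 SD effect and 20 per arm, adjusting for both scores gains about 12 to 19 points of power over the change score. Most of that is baseline adjustment at correlations 0.4 to 0.6; at 0.7 the V2 and V1 shares are about equal (6.0 and 5.6 points). V1's own part is about 0 to 6 points before the cost of estimating its coefficient, and can be slightly negative after it. All sizes rest on assumed inputs. The documents settle the direction for baseline adjustment, but not how much V1 adds.

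**What to change.** In the primary-analysis paragraph under Study Design and under Statistical Analysis, pre-specify the following before unblinding:

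- The model for the MGH-CPFQ total score includes the V2 score and the V1 score as separate continuous covariates, replacing the unadjusted change-score comparison.
- A subject without a V1 score stays in the analysis with V2 alone. State how this is coded, so that the software does not drop the subject.
- The simple V1-V2 mean is not used, because it fixes equal weights and can do slightly worse than V2 alone.
- This model, not the CMH response-rate test, analyses the stated primary endpoint.

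The same rule may be used for other continuous outcome scales scored at both visits, such as the QIDS-16. The MADRS is not scored at V1, so only V2 is available there.

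The cost is a few sentences of wording and two residual degrees of freedom, with no new data. The second covariate also costs about 3% of variance at N = 40 and 5% at N = 24 through estimation. The V2 term is therefore the essential part. With only 24 evaluable subjects the V1 term is a close call, to be decided in advance.

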- 1. Primary outcome: The group treated with MSA adjunctive to ADT will show a greater mean change from baseline to endpoint in total score as compared to the group treated with placebo (PBO) adjunctive to ADT as measured by the
 - a. Massachusetts General Hospital Cognitive-Physical Function Questionnaire (MGH-CPFQ)
- 2. Secondary outcome:
 - a. MSA adjunctive to ADT will demonstrate clinically acceptable safety and tolerability, compared to placebo, based on
 - i. spontaneously reported adverse events and significant adverse events
 - ii. significant changes in blood pressure and pulse
 - iii. significant changes in weight
 - iv. significant changes in electrocardiogram
 - v. significant changes in the Rush Sexual Inventory
 - b. The group treated with MSA adjunctive to ADT will show a greater mean change from baseline to endpoint as compared to the group treated with PBO adjunctive to ADT as measured by the change on
 - i. MGH-CPFQ individual item analysis
 - ii. MADRS scores:
 - 1. Total score
 - 2. Subscales
 - 3. Individual item analysis
 - 4. Percent of "responders" (\geq 50% reduction in score baseline to endpoint)
 - 5. Percent reaching "remission" (score of ≤ 10 at endpoint)

- c. The group treated with MSA adjunctive to ADT will show statistically significant improvement in core residual symptoms of MDD extant on monotherapy ADT as measured by the
 - i. PGI (Patient Impression and Improvement) scales
 - ii. Quick Inventory of Depressive Symptomatology-16 (QIDS-16) total score (≤ 6) and subscale
 - iii. Clinical Global Impression-Severity (CGI-S); and, Clinical Global Impression-Improvement (CGI-I)
 - iv. QIDS total score and subscale
- d. The group treated with MSA adjunctive to ADT will show statistically significantly improvement in overall functioning (work, social and cognitive) when compared to the group treated with PBO and ADT as measured by the
 - i. Total and individual item scores from the HDRS-17 and -28
 - ii. Maier and other subscale scores from the HDRS-17 and -28
 - iii. Scale For Assessment Of Negative Symptoms (SANS)
 - iv. Health Status Questionnaire, 2nd ed. (HSQ 2.0)
 - v. SF-36 Health Survey (SF36)
 - vi. Fawcett Experienced Pleasure Index (EPI)
 - vii. Endicott Work Productivity Scale (EWPS)
 - viii. Sheehan Disability Scale (SDS)
 - ix. Fatigue Associated with Symptoms of Depression (FASD)

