All concomitant medications taken during the study will be recorded in the case report form, along with dosage information and start and stop dates. Subjects requiring excluded drugs will be discontinued from the study. Medication management and clinical ratings will be performed by the study clinicians.

Subjects who complete the trial will be offered referrals to qualified physicians for the purposes of continued care. At the conclusion of Visit 8, study blind will be removed by an unblinded study staff member for facilitation of ongoing treatment by patient's selected follow-up care provider. At Visit 8, study subjects will be provided a one-month prescription for the dose of MSA they are currently prescribed in the study to ease transition to their follow-up care physician.

At the end of the study, subjects will be followed for up to three months while an appointment can be secured with their original treatment provider or with one referred by the research center.

Investigational Product(s), Dose and Mode of Administration, Duration of Treatment with Investigational Product(s): Based upon clinical judgment and ascertained between clinician and patient, study drug will be dosed as follows: The total daily dosage of study drug will be 5-60 mg, supplied in 5 and 10 mg tablets of MSA or matching PBO.

Total daily dosing of the concurrent ADT will be as follows: escitalopram 10-40 mg; fluoxetine 20-80 mg; paroxetine CR 25-100 mg (paroxetine 20-80 mg may be substituted if paroxetine CR is not available); sertraline 100-400 mg; venlafaxine XR 150-600 mg; desvenlafaxine 50-200mg; citalopram 20-80 mg; or duloxetine 60-180 mg; bupropion 150-450 mg; mirtazapine 15-45 mg, tricyclics (standard dosing, individually per label instructions).

The dose of MSA begins at 5mg BID. MSA dose range will be 5mg-20mg BID or TID, not to exceed 60mg per day in addition to the stable dose of ongoing ADT. Each study medication tablet will be 5 or 10 mg of MSA or PBO. Upward titration will be based upon physician's clinical judgment and confirmed by patient's consent.

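### CGI-S change, a key secondary endpoint, has no post-baseline rating; HDRS is first repeated after placebo has ended, and no EKG is scheduled in the placebo phase

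*Combined protocol and SAP*

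**What the plan says.** **Endpoints.** Under Statistical Analysis, Study Assessments and Primary Endpoints, the key secondary endpoints include the "difference in change scores on the CGI-S, CGI-I and QIDS". Research Hypotheses 2c.iii also names CGI-S. Hypothesis 2d claims better functioning "when compared to the group treated with PBO and ADT as measured by the" listed scales, the first being "Total and individual item scores from the HDRS-17 and -28". Hypothesis 2a states that "MSA adjunctive to ADT will demonstrate clinically acceptable safety and tolerability, compared to placebo, based on" a list that includes EKG changes (2a.iv). The Statistical Analysis section lists EKG and physical examination as safety outcomes.

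**Treatment.** Study Procedures, Baseline visit, gives "Group 2: PBO during Phase 1 followed by MSA during phase 2". Phase 1 ends at V5 (day 21), when the Phase 2 drug is dispensed. From then to V8 (day 42) both groups take MSA.

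**Schedule (Fig. 3).** CGI-S and PGI-S are marked at V1 and V2. The row beginning "HDRS (17- and 28-item" is marked at V1, V2 and V8, EKG at V1 and V9, and physical examination at V1.

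**Withdrawals and end of study.** Study Procedures says: "If a subject withdraws or is terminated early from the study, visit 9 procedures will be performed at the final study visit". At V8 taper instructions are given, yet also at V8 "study subjects will be provided a one-month prescription for the dose of MSA they are currently prescribed in the study".

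**The concern.** A change score needs a value after baseline, and a comparison with placebo needs a value taken while one group is still on placebo. Set against Fig. 3, the CGI-S endpoint fails the first requirement, and the HDRS and EKG comparisons fail the second.

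Three things are at stake. A named key secondary endpoint could not be reported. The V8 HDRS contrast would be six weeks of MSA against three, so a null result could be misread as no effect against placebo. Any statement that EKG safety was acceptable relative to placebo would have no randomized data behind it. Ratings that were never scheduled cannot be recovered once the visit has passed.

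**Working it through.** The plan gives no power or sample-size calculation for these outcomes, so there is no stated figure to reproduce. The main check is a count of scheduled assessments.

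**Step 1. Count the marks in Fig. 3.** Each row below has all nine visit cells (V1 to V9).

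| Measure | Visits marked | Placebo phase, V3–V5 | On treatment, V3–V8 |
|---|---|---|---|
| CGI-S | V1, V2 | 0 | 0 |
| PGI-S | V1, V2 | 0 | 0 |
| HDRS-17/28 | V1, V2, V8 | 0 | 1 |
| EKG | V1, V9 | 0 | 0 |
| CGI-I | V3–V8 | 3 | 6 |
| MADRS | V2–V8 | 3 | 6 |
| QIDS-16 | V1–V8 | 3 | 6 |

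The neighbouring CGI-I, MADRS and QIDS-16 rows read normally, so a fault in reading the table is unlikely.

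**Step 2. Can LOCF or the withdrawal rule supply the missing values?** Under Statistical Methods, LOCF carries forward post-randomization data only. Withdrawals receive V9 procedures. The V9 column contains vital signs and weight, EKG, laboratory tests, C-SSRS, drug accountability, concomitant therapy and adverse events. It has no CGI-S and no HDRS. So 0 of 40 subjects have a CGI-S change score, and 0 of 40 have a post-baseline HDRS in the placebo phase. A subject who leaves before V8 has no post-baseline HDRS at all.

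**Step 3. What the V8 HDRS contrast measures.** Assumptions, none of them in the plan: Group 1's standardized effect d is stable from week 3 to week 6, and Group 2 has reached a fraction c of it by V8. The expected V8 contrast is then (1 − c)d. Power uses the noncentral t distribution, two-sided 0.05, df = 2n − 2, noncentrality (1 − c)d√(n/2). The group sizes, 20 randomized and a floor of 12 evaluable per arm, come from Number of Subjects.

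For example, with n = 20, d = 0.8 and c = 0, noncentrality is 0.8 × √10 = 2.53 and power is 69%. With c = 0.5 it is 0.4 × √10 = 1.26 and power is 23%.

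| n per arm | Comparison | d = 0.5 | d = 0.8 | d = 1.0 |
|---|---|---|---|---|
| 20 | V5, if it were rated (c = 0) | 34% | 69% | 87% |
| 20 | V8, c = 0.5 | 12% | 23% | 34% |
| 20 | V8, c = 0.75 | 7% | 9.5% | 12% |
| 20 | V8, c = 1 | 5% | 5% | 5% |
| 12 | V5, if it were rated (c = 0) | 22% | 47% | 65% |
| 12 | V8, c = 0.5 | 9% | 16% | 22% |

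**Step 4. EKG.** V9 is day 56, which is 56 − 21 = 35 days (five weeks) after the placebo phase ends and 56 − 42 = 14 days (two weeks) after V8. Because V8 brings both taper instructions and a one-month prescription, V9 tracings will mix subjects on and off drug. Phase 1 tracings come only from withdrawals. If 5% to 20% withdrew in Phase 1 (an assumption), that is 40 × 0.05 = 2 to 40 × 0.20 = 8 tracings, from a selected group.

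**The case against.** The reading of Fig. 3 is hard to dispute; the case on the other side concerns weight and remedy.

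- **Unequal parts.** Only CGI-S is a key secondary endpoint. HDRS appears under hypothesis 2d and as an entry criterion, and EKG and physical examination are safety listings. This is correct, and CGI-S carries most of the weight.
- **Loose wording.** Fig. 3 pairs severity at V1–V2 with improvement at V3–V8 for both CGI and PGI, so CGI-S may simply have been listed by mistake. CGI-I, MADRS and QIDS-16 cover similar ground at V3–V8. Deleting CGI-S from the list would remove the inconsistency. However, the plan lists CGI-I as a separate endpoint, and it does not yield a severity change.
- **Not specific to HDRS.** The plan never ties its endpoint to V5, and Study Design places the primary outcome at the end of the trial. Any V8 comparison therefore sets six weeks of MSA against three. This stands as a wider problem. What is particular to HDRS is that no V5 value exists to fall back on.
- **Assumed inputs.** d, c and a stable effect are not in the plan. Dosing starts at 5 mg BID and may rise to 60 mg per day, so Group 1 may still be improving after week 3. If its effect grew to g × d, the V8 contrast would be (g − c)d, larger than the table assumes. That weakens the exact percentages, but the contrast would still not be MSA against placebo.
- **EKG on drug.** No EKG is scheduled from V2 to V8, so none is scheduled during the six treatment weeks either. Rewording the hypothesis does not cure that.

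**Conclusion.** The concern holds. The CGI-S change cannot be computed for any subject. The HDRS and EKG comparisons with placebo have no scheduled placebo-phase data. Physical examination, a listed safety outcome, has no scheduled post-baseline assessment. These conclusions follow from the schedule alone and need no assumptions.

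The size of the HDRS dilution does rest on assumed values. Under a stable effect, any catch-up by Group 2 shrinks the V8 contrast. At half catch-up with 20 per arm, power is 12% to 34% for d from 0.5 to 1.0, against 34% to 87% at V5.

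The harm is confined to these outcomes. MGH-CPFQ (primary), MADRS, CGI-I, QIDS-16, PGI-I, vital signs, weight, RSI and adverse events are all collected at V3 to V5. The plan should be corrected, but this point does not threaten the primary outcome's data.

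**What to change.** In Fig. 3 and the matching text:

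1. Add CGI-S and PGI-S at V3–V8, or at least at V5. Each is a one-item rating at visits where CGI-I and PGI-I are already scored. Failing that, delete CGI-S change from the key secondary endpoints.
2. Add HDRS at V5 and name V5 as its placebo-controlled endpoint. Report V8 HDRS as six versus three weeks of MSA. This costs one extra HDRS per subject.
3. Add CGI-S and HDRS to the final visit of anyone withdrawing in Phase 1, so that LOCF has a value to carry. For these subjects the HDRS replaces the V5 rating.
4. Keep the V9 EKG as an end-of-study check and remove EKG from the placebo comparison in hypothesis 2a, which costs nothing. If the comparison is wanted, add an EKG at V5 without moving the V9 one, at one tracing per subject. It would also give Group 1 a scheduled tracing on drug.
5. Drop physical examination from the safety outcomes, at no cost, or schedule an examination at V8 or V9.

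None of this changes the sample size, the number of visits or the primary analysis.
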